9.1.2 Relationship to Investigational Product

The relationship of each AE to the IP should be determined by the investigator using these explanations:

- **Suspected:** A reasonable possibility exists that the IP caused the AE. A suspected AE can be further defined as:
 - *Definite:* Relationship exists when the AE follows a reasonable sequence from the time of IP administration, follows a known response pattern of the drug class, is confirmed by improvement on stopping the IP and no other reasonable cause exists.
 - *Probable:* Relationship exists when the AE follows a reasonable sequence from the time of IP administration, follows a known response pattern of the drug class, is confirmed by improvement on stopping the IP and the suspect IP is the most likely of all causes.
 - *Possible:* Relationship exists when the AE follows a reasonable sequence from the time of administration, but could also have been produced by the subject's clinical state or by other drugs administered to the subject.
- **Not Suspected:** A reasonable possibility does not exist that the IP caused the AE. A not suspected AE can further be defined as:
 - *Not Related:* Concurrent illness, concurrent medication, or other known cause is clearly responsible for the AE, the administration of the IP and the occurrence of the AE are not reasonably related in time, OR exposure to IP has not occurred.

Types of evidence that would suggest a causal relationship between the IP and the AE include: a single occurrence of an event that is uncommon and known to be strongly associated with IP exposure (eg, angioedema, hepatic injury, Stevens-Johnson Syndrome); one or more occurrences of an event that is not commonly associated with IP exposure, but is otherwise uncommon in the population exposed to the IP (eg, tendon rupture); an aggregate analysis of specific events observed in a clinical trial (such as known consequences of the underlying disease or condition under investigation or other events that commonly occur in the study population independent of drug therapy) that indicates those events occur more frequently in the IP-treatment group than in a concurrent or historical control group.

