The relationship of each adverse event to the investigational product should be determined by the investigator (in a blinded manner) using these explanations:

- *Definite*: Relationship exists when the AE follows a reasonable sequence from the time of IP administration, follows a known response pattern of the drug class, is confirmed by improvement on stopping the IP and no other reasonable cause exists.
- *Probable*: Relationship exists when the AE follows a reasonable sequence from the time of IP administration, follows a known response pattern of the drug class, is confirmed by improvement on stopping the IP and the suspect IP is the most likely of all causes.
- *Possible*: Relationship exists when the AE follows a reasonable sequence from the time of administration, but could also have been produced by the subject's clinical state or by other drugs administered to the subject.
- *Not Related*: Concurrent illness, concurrent medication, or other known cause is clearly responsible for the AE, the administration of the IP and the occurrence of the AE are not reasonably related in time, OR exposure to IP has not occurred.
- *Unclassified*: When the causal relationship is not assessable for whatever reason due to insufficient evidence, conflicting data or poor documentation.

All possible, probable, and definite TEAEs are considered as treatment-related TEAEs.

All AEs will be presented in a subject listing that classifies each AE as ocular or non-ocular and indicates whether it is a TEAE. Separate listings will be produced for AEs leading to study discontinuation, AEs leading to death and SAEs.

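### As worded, the SAP's causality grades give no related grade to some plausibly timed AEs with no other identified cause, so these can drop out of the treatment-related tables

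*SAP*

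**What the plan says.** SAP 15.1 lists five causality grades and then fixes which of them count: "All possible, probable, and definite TEAEs are considered as treatment-related TEAEs". Those events fill Table 14.3.1.6 (ocular) and Table 14.3.1.7 (non-ocular).

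The grades, all of which the investigator assigns masked, are:

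- **Definite**: plausible timing, and the event "follows a known response pattern of the drug class, is confirmed by improvement on stopping the IP and no other reasonable cause exists".
- **Probable**: plausible timing, a class pattern, and the event "is confirmed by improvement on stopping the IP and the suspect IP is the most likely of all causes".
- **Possible**: plausible timing, "but could also have been produced by the subject's clinical state or by other drugs administered to the subject".
- **Not Related**: another known cause is clearly responsible, the timing does not fit, or the subject was not exposed.
- **Unclassified**: "When the causal relationship is not assessable for whatever reason due to insufficient evidence, conflicting data or poor documentation".

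Protocol 9.1.2 words the first four grades the same way; its Probable, for example, also asks that the event "follows a known response pattern of the drug class, is confirmed by improvement on stopping the IP and the suspect IP is the most likely" cause. It differs from the SAP in two respects. It places Definite, Probable and Possible under a parent category, Suspected, introduced by "A reasonable possibility exists that the IP caused the AE. A suspected AE can be further defined as", with Not Related as the only grade listed under Not Suspected. And it has no Unclassified grade.

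SAP section 1 says that its statistical methods supersede those of the protocol. SAP section 17 states that nothing has changed from the protocol's analyses.

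**The concern.** A causality scale should give every event a place, and stronger evidence of a drug effect should not earn a weaker grade. Here the two upper grades each demand a known class pattern and observed improvement on stopping. The lowest related grade does not ask for either, but it is described by the presence of a competing explanation. An event that follows dosing, has no competing explanation and misses one of the two conditions falls between them.

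Read literally, the ordering then runs backwards. An event with a rival cause is Possible and is counted. The same event without a rival cause has no related grade and can be left out. In a Phase 2 trial whose only described clinical background is one Phase 1 study of two instillations in one day (protocol 1.2), the treatment-related tables are a natural place to look for early signals, so their counting rule should not depend on this accident of wording.

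**Working it through.** No figure in either document bears on this point, so the check is to run every type of event through the literal definitions.

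**Inputs** (SAP 15.1; same wording for the first four grades in protocol 9.1.2). For an exposed subject, four features decide the grade:

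- timing plausible: yes or no (2)
- known class pattern: yes or no (2)
- improvement on stopping shown: yes or no, where no includes dosing that was never stopped (2)
- other cause: none, plausible with the IP most likely, plausible with the IP not most likely, or clearly responsible (4)

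That gives 2 × 2 × 2 × 4 = 32 profiles. Unclassified is set aside as the residual.

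**Results.**

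- Timing not plausible: 16 profiles, all Not Related.
- Timing plausible, other cause clearly responsible: 2 × 2 = 4 profiles, all Not Related.
- Timing plausible, other cause plausible: 2 × 2 × 2 = 8 profiles, all at least Possible, so all counted.
- Timing plausible, no other cause: 2 × 2 = 4 profiles, as follows.

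| Class pattern | Improvement on stopping shown | Grade met |
|---|---|---|
| yes | yes | Definite (Probable also fits) |
| yes | no | none |
| no | yes | none |
| no | no | none |

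Check: 16 + 4 + 8 + 4 = 32. Three profiles meet none of Definite, Probable, Possible or Not Related, and all three have plausible timing and no other cause. Either missing condition is enough to open the gap.

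**Where those three go.** Under protocol 9.1.2 the parent category catches them: a reasonable possibility of causation requires neither a class pattern nor improvement on stopping. Under SAP 15.1 that category is absent and only the three sub-grades count. The one grade left is Unclassified. It fits loosely, and best where the lack of an observed stop is treated as insufficient evidence. It is not counted in Tables 14.3.1.6 and 14.3.1.7.

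**Protocol against SAP.** Protocol 10.4.7 asks for treatment-related AEs by system organ class and preferred term without defining the term, so Suspected in 9.1.2 is the protocol's nearest definition. The SAP substitutes a narrower one and adds a grade, and section 17 records neither step.

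**The case against.** The case against giving this weight is substantial.

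- **Investigators grade by judgement.** Protocol 9.1.2 says that a suspected AE can be further defined by the sub-grades, and it lists evidence for causation that does not depend on improvement after stopping. An investigator reading it would have grounds to choose Possible, and then nothing is lost. This stands: events can fall outside the tables, but the text does not show that they will.
- **No event disappears.** All TEAEs are tabulated regardless of causality (Tables 14.3.1.4 and 14.3.1.5, and by severity and onset in 14.3.1.9 to 14.3.1.12). SAEs have Table 14.3.1.8, and every AE is listed. The masked comparison of all TEAEs between arms does not use these grades. This stands and limits the point to one descriptive subset.
- **Ocular symptoms are mostly safe.** A reader might infer that stinging at each drop would vanish from the related tables. The documents do not support that. Stinging and burning are rated symptoms of the disease under study (SAP 14.2.7 and 14.2.8), so the clinical-state clause of Possible is easily met and the event is counted.

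A reader might also infer that clearly drug-caused events are excluded, or that the gap will be met often. Neither is established. An event with no other identified cause is not thereby proven to be drug-caused. The class condition refers to the drug class, and protocol 1.3 describes approved anti-TNF products, so limited experience with HL036 itself does not make class patterns unknown. Protocol 9.5 has unresolved AEs followed, so improvement after the end of dosing may be seen for some. Three of 32 counts logical profiles and says nothing about frequency.

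None of this repairs the definition. It leaves the SAP's counting rule resting on investigators not applying the wording literally.

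**Conclusion.** Wrong as written, minor. By the literal text of SAP 15.1, a plausibly timed AE with no other identified cause has a related grade only if it shows both a known class pattern and improvement on stopping. The other three combinations have none and can be left as Unclassified, outside Tables 14.3.1.6 and 14.3.1.7. Protocol 9.1.2 would treat such events as Suspected, so the loss arises from the SAP dropping that category, adding Unclassified and declaring no changes.

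The number of affected events cannot be estimated from the documents. It is zero if investigators choose Possible in every such case. It is largest for events with a novel pattern or no reversal that the clinical-state clause does not reach. The conclusion assumes that Possible is read as requiring an alternative cause and that Unclassified is used as the residual grade. It does not affect the all-TEAE or SAE tables or any efficacy analysis.

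**What to change.** 1. In SAP 15.1, before unmasking, define treatment-related TEAEs by the protocol's Suspected category. Equivalently, count every TEAE not graded Not Related, including Unclassified. Because Not Related is the only grade under Not Suspected in protocol 9.1.2, its complement reproduces the protocol's split from grades already collected.
2. Where grading guidance can still be changed, reword Possible in SAP 15.1, protocol 9.1.2 and the eCRF guidance so that it covers a plausibly timed event whether or not another cause could have produced it.
3. Reconcile SAP 15.1 with protocol 9.1.2 on Suspected and Unclassified, and record in section 17 whatever difference is kept.

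The cost of step 1 is one sentence in the SAP and one derivation, with no new data collection. The downside is that slightly more events may be counted as treatment-related, including some Unclassified ones that truly cannot be assessed.

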descriptively (n, mean, standard deviation, median, min and max) by visit and treatment group, and analyzed with two-sample t-tests comparing each of the active treatment groups to placebo. All visit-based data will be analyzed at each visit and change from baseline. Change scores from pre- to post-CAE® will be calculated as Post-CAE® score – Pre-CAE® score. A Wilcoxon rank sum test and an ANCOVA model adjusting for baseline and site will also be assessed where appropriate. No imputation will be performed for secondary efficacy variables.

Fluorescein staining by region and total, Lissamine green staining by region, TFBUT, conjunctival redness, unanesthetized Schirmer's test, Drop comfort assessment, OSDI, ocular discomfort and dry eye symptoms, ocular discomfort during CAE®, pre- to post-CAE® changes, and changes from baseline in these measures will be analyzed by visit using two-sample t-tests and Wilcoxon rank sum tests, as appropriate.

The worst symptom for each subject will be identified as the symptom with the highest average score during the run-in period (Days -14 to -1) as recorded in the subject diary. The worst symptom and each individual symptom will be analyzed per day using a two-sample t-test. Additionally, the average score for the worst symptom and each individual symptom will also be analyzed separately using a Wilcoxon rank sum test.

Safety Variables

Adverse events will be coded using the MedDRA dictionary. Frequencies and percentages of subjects with treatment-emergent adverse events (TEAEs), serious TEAEs, and TEAEs causing premature discontinuation will be provided by treatment group. An AE is treatment emergent if it occurs or worsens after the first dose of study treatment. Furthermore, frequencies will be given of subjects with TEAEs by system organ class, by system organ class and preferred term, by system organ class, preferred term and maximal severity, by system organ class, preferred term and strongest relationship, and by system organ class, preferred term, maximal severity, and strongest relationship. Separate analyses will be performed for ocular specific and all AEs (including systemic).

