10.4.7 Safety Variables

Adverse events will be coded using the MedDRA dictionary. Frequencies and percentages of subjects with treatment-emergent adverse events (TEAEs), serious TEAEs, and TEAEs causing premature discontinuation will be provided by treatment group. An AE is treatment emergent if it 1) occurs after the first dose of randomized study treatment or 2) if it is present prior to receipt of randomized study treatment but worsens in severity or increases in frequency after the first dose of randomized study treatment. Furthermore, frequencies will be given of subjects with TEAEs by system organ class and preferred term; by system organ class, preferred term and maximal severity; by system organ class, preferred term for treatment-related AEs; by system organ class and preferred term for SAEs; and by system organ class, preferred term, and day of onset. Separate analyses will be performed for ocular specific and all AEs (including systemic).

Other safety endpoints including visual acuity, slit lamp biomicroscopy, dilated fundoscopy, and intraocular pressure, will be summarized by treatment group and visit using descriptive statistics. Changes or shifts from baseline will also be summarized where appropriate. For assessments performed by eye, study eye and fellow eye will be summarized separately. In addition, shifts from baseline to worst on-treatment value for ocular safety assessments will be summarized.

Immunogenicity will be summarized using discrete summary statistics. Counts and proportions will be presented by visit and treatment group. Exact 95% Clopper-Pearson confidence intervals will be presented. Treatment groups will be compared using Fisher's Exact Test, and exact 95% confidence intervals for the pairwise proportion differences will be constructed.

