TABLE 14.2.3.9	ORA CALIBRA® OCULAR DISCOMFORT & 4-SYMPOTM QUESTIONNAIRE FOR DRY EYE (DIARY)	ITT WITH OBSERVED DATA ONLY
TABLE 14.2.3.10	VISUAL ANALOGUE SCALE	ITT WITH OBSERVED DATA ONLY
TABLE 14.2.3.11	OCULAR SURFACE DISEASE INDEX (OSDI)®	ITT WITH OBSERVED DATA ONLY
TABLE 14.2.3.12	ORA CALIBRA® DROP COMFORT SCALE	ITT WITH OBSERVED DATA ONLY
TABLE 14.2.3.13	ORA CALIBRA® DROP COMFORT QUESTIONNAIRE	ITT WITH OBSERVED DATA ONLY
TABLE 14.3.1.1	ADVERSE EVENT SUMMARY	SAFETY
TABLE 14.3.1.2	ALL OCULAR ADVERSE EVENTS	SAFETY
TABLE 14.3.1.3	ALL NON-OCULAR ADVERSE EVENTS	SAFETY
TABLE 14.3.1.4	ALL OCULAR TREATMENT-EMERGENT ADVERSE EVENTS	SAFETY
TABLE 14.3.1.5	ALL NON-OCULAR TREATMENT-EMERGENT ADVERSE EVENTS	SAFETY
TABLE 14.3.1.6	ALL OCULAR TREATMENT-RELATED TREATMENT-EMERGENT ADVERSE EVENTS	SAFETY
TABLE 14.3.1.7	ALL NON-OCULAR TREATMENT-RELATED TREATMENT-EMERGENT ADVERSE EVENTS	SAFETY
TABLE 14.3.1.8	ALL SERIOUS ADVERSE EVENTS	SAFETY
TABLE 14.3.1.9	ALL OCULAR TREATMENT-EMERGENT ADVERSE	SAFETY

Table Number	Title	Population
	EVENTS BY MAXIMAL SEVERITY	
TABLE 14.3.1.10	ALL NON-OCULAR TREATMENT-EMERGENT ADVERSE EVENTS BY MAXIMAL SEVERITY	SAFETY
TABLE 14.3.1.11	ALL OCULAR TREATMENT-EMERGENT ADVERSE EVENTS BY STUDY DAY OF ONSET	SAFETY
TABLE 14.3.1.12	ALL NON-OCULAR TREATMENT-EMERGENT ADVERSE EVENTS BY STUDY DAY OF ONSET	SAFETY
TABLE 14.3.2	BEST CORRECTED VISUAL ACUITY - LOGMAR	SAFETY
TABLE 14.3.3.1	SLIT LAMP BIOMICROSCOPY	SAFETY
TABLE 14.3.3.2	SHIFT IN SLIT LAMP BIOMICROSCOPY	SAFETY
TABLE 14.3.4.1	DILATED FUNDOSCOPY	SAFETY
TABLE 14.3.4.2	SHIFT IN DILATED FUNDOSCOPY	SAFETY
TABLE 14.3.5	INTRAOCULAR PRESSURE	SAFETY
TABLE 14.3.6	COMPLIANCE WITH STUDY DRUG	SAFETY
TABLE 14.3.7	EXPOSURE TO STUDY DRUG	SAFETY

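### SAP 15.1 adds an undeclared Unclassified causality grade; its rule leaves those events out of the treatment-related tables, which could understate related events if the grade is used

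*SAP*

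**What the plan says.** **Protocol 9.1.2** sorts causality into two classes. Suspected opens with "A reasonable possibility exists that the IP caused the AE. A suspected AE can be further defined as" and covers definite, probable and possible. Not Suspected opens with "A reasonable possibility does not exist that the IP caused the AE. A not suspected AE can further be defined as" and has a single grade, not related. There is no grade for an event that cannot be assessed.

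**SAP 15.1** keeps the four grades, drops the two class headings and adds Unclassified, which applies "When the causal relationship is not assessable for whatever reason due to insufficient evidence, conflicting data or poor documentation". It presents the whole list as the one the investigator uses, while masked. The counting rule follows: "All possible, probable, and definite TEAEs are considered as treatment-related TEAEs".

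**Tables.** Protocol 10.4.7 plans a summary "by system organ class, preferred term for treatment-related AEs". The SAP delivers it as Table 14.3.1.6 ("ALL OCULAR TREATMENT-RELATED TREATMENT-EMERGENT ADVERSE EVENTS") and its non-ocular counterpart, Table 14.3.1.7. The protocol synopsis also plans a breakdown by "preferred term and strongest relationship". Neither protocol 10.4.7 nor the table list in SAP 19 includes one.

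**Declared changes.** SAP 17 reports no departures from the analyses in the protocol.

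**The concern.** In the protocol, Not Suspected is an affirmative judgment: "A reasonable possibility does not exist that the IP caused the AE". An event with poor documentation or conflicting data does not meet that test. The SAP gives such an event its own grade but says nothing about how it is counted. Because the related-event rule lists only three grades, a non-assessable event drops out of the related tables by omission, not by a stated decision.

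The boundary between grades also shifts. An event with plausible timing and a competing explanation fits the protocol's description of possible, and would count as related. Under the SAP the same event could be called Unclassified because the evidence conflicts, and would not count. Compared with counting these events as related, leaving them out can lower an arm's related rate but never raise it.

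At stake are two descriptive safety tables. They carry some weight because the only earlier clinical study described in protocol 1.2 dosed healthy male volunteers twice in one day, whereas this trial treats patients for eight weeks. The efficacy analyses are untouched.

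**Working it through.** The plan states no figure for this point, so there is nothing to reproduce. The check compares the two texts and then gives a short illustration.

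**Step 1. The two scales, and whether each grade counts as related**

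| Grade | Protocol 9.1.2 | SAP 15.1 | In Tables 14.3.1.6 and 14.3.1.7 under the SAP rule |
|---|---|---|---|
| Definite | Suspected | Listed | Yes |
| Probable | Suspected | Listed | Yes |
| Possible | Suspected | Listed | Yes |
| Not related | Not Suspected | Listed | No |
| Unclassified | Absent | Listed | No; not named in the rule |

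Four grades have become five. The fifth has no counterpart in the protocol and no counting rule in the SAP.

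**Step 2. Where an Unclassified TEAE still appears (SAP 15.1, 19 and 20)**

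- Overall summary: Table 14.3.1.1.
- All ocular and non-ocular TEAEs: Tables 14.3.1.4 and 14.3.1.5.
- By maximal severity: Tables 14.3.1.9 and 14.3.1.10.
- By day of onset: Tables 14.3.1.11 and 14.3.1.12.
- If serious: Table 14.3.1.8.
- Listing of all adverse events: Listing 16.2.7.1.

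It is missing only from the two treatment-related tables. No planned table shows Unclassified events on a row of their own. A breakdown by strongest relationship, as in the protocol synopsis, would have been the natural place.

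**Step 3. Illustration of size**

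Inputs: n = 50 subjects per arm (SAP 6), assumed here to be the Safety population denominator; k = subjects in an arm with an Unclassified TEAE and no TEAE graded possible, probable or definite. The documents give no value for k, so a range is shown.

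Drop in the arm's related rate, compared with counting these subjects as related = 100 × k / n = 100 × k / 50 = 2k percentage points.

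| k | Drop (percentage points) |
|---|---|
| 0 | 0 |
| 1 | 2 |
| 2 | 4 |
| 5 | 10 |

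**Step 4. Active minus placebo**

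With k_A such subjects in an active arm and k_P on placebo, leaving them out changes the difference in related rates by −2 × (k_A − k_P) points. For k_A = k_P the change is 0. For k_A = 2 and k_P = 0 the difference falls by 4 points; for k_A = 0 and k_P = 2 it rises by 4.

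**The case against.** The strongest reply is that nothing is shown to be understated.

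- **The grade may never be used.** Investigators work from the protocol, which offers four grades. SAP 1 gives the SAP precedence over the protocol's statistical methods, not over how investigators grade events. The eCRF options are not in the documents. This stands, though SAP 15.1 does present its five-grade list as the investigator's, so the two texts conflict.
- **A non-assessable event is not known to be drug-related.** A reader might infer that the related tables will be too low as a matter of fact. The documents do not support that: it needs both that the grade is used and that some of the events so graded are related. This stands, and the point is worded conditionally for that reason.
- **The SAP does not call these events not related.** A reader might infer that it reclassifies them as such. It keeps the two grades apart and plans no table of unrelated events. What can be said is narrower: Unclassified events fall outside the related tables and have no row elsewhere.
- **The events are not lost.** This stands, as Step 2 shows.
- **No bias between arms follows.** Grading is masked and the rule is the same in every arm. This stands; Step 4 shows that the contrast can move either way.
- **The synopsis breakdown by strongest relationship was already absent from protocol 10.4.7**, so the SAP follows the protocol body there. This also stands, and no weight is put on that omission as a SAP departure.

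None of this removes the mismatch between the scales, the missing counting rule, or the silence in SAP 17.

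**Conclusion.** The concern holds as a minor, undeclared inconsistency with a possible effect in one direction on each arm's related-event rate. SAP 15.1 has a causality grade that protocol 9.1.2 lacks, and its rule leaves that grade out of Tables 14.3.1.6 and 14.3.1.7 without saying so. If the grade is used, those tables could understate related events by 2k percentage points per arm, assuming 50 subjects per arm and k subjects whose only candidate related TEAE is Unclassified. That range starts at zero, and the documents give no basis for choosing a value within it. A demonstrated understatement, a loss of events from safety reporting and a bias between treatments are all stronger readings that the text does not bear out. The change is worth making because it is cheap and because a counting rule settled after unmasking would be chosen with treatment known.

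**What to change.** Before unmasking:

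1. Check which causality options the eCRF offers and whether any event has been recorded as Unclassified. Deleting the grade from the SAP alone solves nothing if the eCRF allows it.
2. Align the two scales in one of two ways:
   - remove Unclassified from SAP 15.1 so that it matches protocol 9.1.2; or
   - keep it, state that Unclassified TEAEs count as treatment-related in Tables 14.3.1.6 and 14.3.1.7, and show their number separately so that a reader can see the result with and without them.
3. If the grade is kept, record the difference from the protocol in SAP 17.

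The cost is a sentence or two in the SAP, plus a row or footnote in two tables if the grade stays. The downside is that the treatment-related rate may look slightly less favourable, in any arm including placebo, and may include some events that the drug did not cause. The separate count lets the reader judge that.
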